### 9.8.5 *Patient replacement*

Patients who are prematurely withdrawn from the study for any reason except the occurrence of AEs assessed as possibly or probably related to study treatment may be replaced during the course of the study.

## 9.9 Randomization

On Day 1, patients will be randomized to receive either NLX-112 or placebo. The randomization will be performed per site using SAS with the ratio 2:1 for active treatment to placebo. This will give approximately 16 patients receiving NLX-112 and 8 patients receiving

placebo in total in the study. In addition, approximately the same ratio will be attained within each site. The study will use competitive enrollment between sites.

## **9.10 Blinding**

This is a double-blind study and the allocation of treatments will not be disclosed until clean file has been declared and the database has been locked.

The IMP and the placebo are identical in appearance and taste.

## **9.11 Emergency unblinding during the study**

The treatment code may only be broken by the Principal Investigator or delegate in case of emergency when knowledge of the treatment received is necessary for the proper medical management of the patient. This will either be performed via the EDC system or using sealed individual, treatment code envelopes that are kept at the clinic in a locked and restricted area. The code breaking procedure should be carefully documented.

For unblinding procedures in case of a potential suspected unexpected serious adverse reaction (SUSAR), refer to Section 11.2.1.14.

# **10 TREATMENTS**

## **10.1 Identity of investigational medicinal products**

NLX-112 will be supplied as tablets containing 0.25 mg NLX-112.

Placebo will be matching tablets (identical weight, shape and color) without NLX-112.

## **10.2 Manufacturing, packaging and labelling**

The IMP, including placebo, is manufactured by Sharp Clinical, Bethlehem, United States.

Labels will comply with applicable Good Manufacturing Practice (GMP), with Annex 13 of the European Union GMP regulations and local regulatory requirements [23].

## **10.3 Importation, release and distribution**

The IMP will be imported, released and distributed by ClinStorage, Solna, Sweden.

## **10.4 Conditions for storage**

All study drug must be stored and disposed of according to the Sponsor's instructions. Study drug must be stored at the study site in a limited-access area or in a locked cabinet at ambient room temperature.

Temperature logs will be kept for the area where the IMP is stored. The temperature should be noted on a daily basis (working days only unless automatic temperature readings are available).

IMP that is brought home by the patients should be stored at room temperature.

## **10.5 Dispensing and accountability**

The IMP received at the site must be inventoried and accounted for throughout the study. The Investigator will maintain a Storage and Accountability Log as well as a Drug Dispensing Log detailing the dates and quantities of study medication received, prepared for and used by each patient and study medication returned or destroyed at the end of the study. Patients must be instructed to return all original containers, whether empty or containing drug.

Unused study drug, and study drug returned by the patient, must be available for verification by the study site monitor during on-site monitoring visits. Any discrepancies between prepared and returned study must be explained and documented. Products deliberately and/or accidentally destroyed by the site or the patient must be accounted for.

Study drug must be dispensed under the supervision of the Investigator or qualified designee, or by a hospital/clinic pharmacist.

At Visits 2, 6 and 7 (Day 1, Day 28, and Day 42) patients will be provided with a small bottle of tablets with explicit dosing instructions, including a dosing instruction sheet as well as a worksheet to keep track of daily doses. The bottle will contain sufficient drug supplies to last until the next scheduled clinic visit. Patients will return the previously used bottle at the next clinic visit including any unused IMP.

## **10.6 Treatment administration**

Patients will self-administer NLX-112 or placebo 2 times each day, once in the morning and once in the evening, according to a dosing instruction sheet. Tablets should be taken with approximately 240 mL water during a meal.

## **10.7 Continuation of treatment with investigational medicinal product**

There will be no treatment with NLX-112 after end of study participation.

## **10.8 Treatment compliance**

Patients will self-administer the IMP at home. At each visit to the clinic, patients will be asked to return any unused IMP and all empty/partially used IMP containers.

Treatment compliance may also be addressed by NLX-112 plasma concentration measurements at visits outlined in Table 8.1-1.

## **10.9 Return and destruction of investigational medicinal products**

Following confirmation by the Sponsor, any unused study medication will be returned to ClinStorage AB, Solna, Sweden for destruction or subsequent return to the Sponsor. Empty containers will be destroyed at the study site. The Monitor will perform final IMP accountability reconciliation at the study end to verify that all unused IMP is adequately destroyed/returned and documented.

## 11 STUDY ASSESSMENTS

The study assessments are described in the sections below and the timing of these assessments are detailed in the schedule of events (Table 8.1-1)

### 11.1 Recording of data

The Principal Investigator will provide the Sponsor with all data produced during the study from the scheduled study assessments. He/she ensures the accuracy, completeness, legibility, and timeliness of the data reported to Sponsor in the eCRF and in all required reports.

#### 11.1.1 *Informed consent*

Signed informed consent must be obtained before any screening procedures are initiated. The informed consent procedure is further described in Section 14.3.

#### 11.1.2 *Eligibility criteria*

Eligibility criteria should be checked during screening and verified before randomization. The criteria are specified in Sections 9.4 and 9.5.

#### 11.1.3 *Demographic information*

The following demographic data will be recorded: gender, age, ethnicity and race.

#### 11.1.4 *Weight and height*

Weight and height will be measured with the patient wearing light clothes and no shoes. Body mass index (BMI) will be calculated, with one decimal, from the height and weight recorded.

#### 11.1.5 *Medical and psychiatric history*

A complete medical and psychiatric history will include evaluation for past or present cardiovascular, respiratory, gastrointestinal, renal, hepatic, neurological, endocrine, metabolic, lymphatic, hematologic, immunologic, dermatologic, psychiatric, genitourinary, drug, and surgical history, or any other diseases or disorders (including past diagnosis of HIV or hepatitis B/C).

As part of the medical history at screening, patients will be evaluated using the C-SSRS (Section 11.2.5), which will be scored by the Investigator to confirm the patient's eligibility for the study.

#### 11.1.6 *Prior and concomitant medication*

Medications taken within 4 weeks of the screening visit (Visit 1) will be obtained by patient interview.

Medications are classified as prior if the stop date was before or on the day of the first dose administration (pre-dose) and as concomitant if ongoing on the day of the first dose administration, stopped after the first dose administration or started after the first dose administration. To distinguish between prior and concomitant medications on Day 1 (i.e. the

first dosing day), the start time of any newly introduced medication or the stop time of any previously ongoing medication must be recorded in the eCRF.

Any use of prior or concomitant medication from screening until the last end-of-study visit must be documented appropriately in the patient's eCRF. Relevant information (*i.e.* name of medication, dose, dose form, unit, route, frequency, start and stop dates, reason for use) must be recorded. All changes in medication should be noted in the eCRF.

#### **11.1.7 *Pregnancy test***

All women of child-bearing potential will do a urine pregnancy test at screening (Visit 1) and at baseline (Visit 2).

#### **11.1.8 *Hoehn and Yahr scale***

The Modified Hoehn and Yahr scale will be used to establish the PD stage of the patient. The modified scale includes 7 stages (1, 1.5, 2, 2.5, 3, 4 and 5) where stage 1 corresponds to unilateral involvement only and 5 to wheelchair bound or bedridden unless aided.

#### **11.1.9 *Mini Mental Status Exam***

The Mini Mental Status Exam (MMSE) is a 30-point questionnaire used to measure cognitive impairment. The MMSE will be used to screen for dementia. Any score of 24 or more (out of 30) indicates a normal cognition. Below this, scores can indicate severe ( $\leq 9$  points), moderate (10–18 points) or mild (19–23 points) cognitive impairment.

#### **11.1.10 *Baseline symptoms***

A baseline symptom is defined as an event that occurs between the patient's signing of the ICF until the first administration of IMP (*i.e.* an event that occurs during the screening period). Such events are not AEs and will be recorded as baseline symptoms in the Medical History Log in the eCRF.

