**Safety assessments**

Safety/tolerability assessments will include: medical history (screening), physical examination (screening and follow-up), 12-lead ECG (all clinic visits), vital signs (all clinic visits), AEs (from baseline visit through follow up visit), assessment of suicidal ideation/behavior (C-SSRS; all clinic visits), and clinical labs (hematology, blood chemistry, and urinalysis; all clinic visits).

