13. Collection of AEs from the first dose of IMP.

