## 8.2 Order of assessments

Safety assessments should be performed before the L-DOPA challenge at Visit 2, 6 and 7.

The efficacy assessments at Visits 2, 6 and 7 should be performed in the order outlined in Table 8.2-1.

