##### **11.2.1.1 *Definition of adverse event***

An AE is defined as any untoward medical occurrence in a patient administered a medicinal product and which does not necessarily have a causal relationship with this treatment. An AE can therefore be any unfavorable and unintended sign (including an abnormal laboratory finding), symptom, or disease temporally associated with the use of a medicinal product, whether or not considered related to the medicinal product.

Worsening of dyskinesias (except those associated with the 150% L-DOPA challenge) or PD symptoms compared to baseline will be reported as AEs.

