#### *11.2.1.6 Time period and frequency for collecting adverse events*

All AEs (including SAEs) will be collected from the start of IMP administration until the end-of-study visit.

Any AE with start date on the day of IMP administration will, if possible, be recorded with start time.

At the end-of-study visit, information on new AEs or SAEs, if any, and stop dates for ongoing events must be recorded as applicable.

Investigators are not obligated to actively seek AEs or SAEs after conclusion of the study participation. However, if the Investigator learns of any SAE, including a death, at any time after a participant has been discharged from the study, and he/she considers the event to be reasonably related to the study intervention or study participation, the Investigator must promptly notify the Sponsor.

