### 11.3.1 **L-DOPA challenge**

The patient will take 150% of their normal L-DOPA dose 30 minutes prior to the start of efficacy assessments (UDysRS) at Day 1 (Visit 2), Day 28 (Visit 6) and Day 42 (Visit 7), see Table 8.1-1 and Section 11.3.2.

The challenge should be performed approximately 2 to 2.5 hours after the patient's morning dose (which is also generally around 150%).

Patients who use continuous intestinal levodopa infusion (Duodopa or Lecigon) should instead stop the infusion for 15-30 minutes before the administration of an oral levodopa dose equivalent to 300% of their hourly infusion levodopa equivalent dose (LED\*). The time of the day and the time between stopping the pump and administering the oral dose should be the same on all assessments.

\*) 100 mg Duodopa = 111 mg LED, 100 mg Lecigon = 148 mg LED

The maximum L-DOPA dose to be given is 250 mg.

The UDysRS (Parts III and IV) will be repeated 3 times after each L-DOPA challenge, 30 minutes apart, and will hence be performed approximately 30, 60 and 90 minutes after each challenge.

Should the Investigator consider it medically warranted to reduce the L-DOPA challenge in a specific patient for safety or tolerability reasons, this should be approved by the Sponsor prior to implementation. It is critical that the same dose is given at all visits with L-DOPA challenges for a given patient.

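### AE and SAE collection opens at the first IMP dose, so harm starting between the Visit 2 L-DOPA challenge and that dose is not reportable, and the challenge-dyskinesia exemption at Visits 6 and 7 has no stated limit for serious cases

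*Protocol*

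**What the plan says.** **When collection starts.** Protocol Section 11.2.1.6 states: "All AEs (including SAEs) will be collected from the start of IMP administration until the end-of-study visit". Footnote 13 of Table 8.1-1 agrees: "Collection of AEs from the first dose of IMP". Section 11.1.10 covers the time from consent to first IMP administration: "Such events are not AEs and will be recorded as baseline symptoms in the Medical History Log in the eCRF". The synopsis, under Safety assessments, gives a different start: "AEs (from baseline visit through follow up visit".

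**The challenge.** Section 11.3.1 places a challenge on Day 1 (Visit 2), Day 28 (Visit 6) and Day 42 (Visit 7), capped at 250 mg. It foresees individual safety problems: "Should the Investigator consider it medically warranted to reduce the L-DOPA challenge in a specific patient for safety or tolerability reasons", the Sponsor must approve first. It also treats giving a patient the same dose at every challenge visit as critical.

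**The exemption.** Section 11.2.1.1 reads: "Worsening of dyskinesias (except those associated with the 150% L-DOPA challenge) or PD symptoms compared to baseline will be reported as AEs". Section 11.2.1.2 defines an SAE as a kind of AE, namely one that meets a seriousness criterion.

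**Timing of other safety checks.** Section 8.2 says: "Safety assessments should be performed before the L-DOPA challenge at Visit 2, 6 and 7".

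**The concern.** The challenge is a study procedure that administers a drug, and the AE definition in Section 11.2.1.1 refers to medicinal products in general, not to the IMP alone. One would expect serious harm from it to reach the sponsor through the SAE route. Under the body text, the first challenge in each patient falls before that route opens. A syncope or a fall with fracture after the Visit 2 challenge and before the first tablet would be entered in the Medical History Log with no alert, although the same challenge is to be given twice more.

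At Visits 6 and 7 the route is open but has a gap. Challenge dyskinesia is carved out of the AE definition without a seriousness limit. Frequency, intensity and seriousness of AEs are a primary endpoint, so a serious dyskinesia event on study treatment could be missing from it.

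**Working it through.** The plan states no figure on this point. The check is a comparison of sections plus one count.

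**Step 1: order of events at Visit 2.** The protocol gives no clock order for Day 1.
- Protocol Section 17.1 and SAP Section 5.5 define baseline as the latest available value before any IMP is taken.
- Protocol Section 11.3.2 schedules the baseline UDysRS at Visit 2, starting about 30 minutes after the challenge.
- If the tablet came first, the Visit 2 UDysRS could not be the baseline. The challenge therefore precedes the first dose. This is an inference, but the efficacy analysis depends on it.

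**Step 2: status of an event between challenge and first tablet.**

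| Source | Is it an AE or SAE? |
|---|---|
| Protocol 11.1.10 | No; medical history |
| Protocol 11.2.1.6 | No; the window is not yet open, for SAEs either |
| Protocol Table 8.1-1, footnote 13 | No |
| Protocol synopsis, Safety assessments | Yes; the window opens at the baseline visit |

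None of the first three has an exception for serious or procedure-related events. Without AE status there is no intensity grade (11.2.1.7), no causality rating (11.2.1.8) and no 24-hour report (11.2.1.13).

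**Step 3: status of an event after the challenge at Visits 6 and 7.** The patient is on IMP and the window is open.
- Harm other than worsening dyskinesia, including an injury caused by dyskinesia, is an AE, and an SAE if it meets a criterion.
- Worsening dyskinesia tied to the challenge is not an AE. Since every SAE must first be an AE, the literal reading is that a serious case is not an SAE. The protocol does not say this outright.
- Section 11.2.1.8 rates causality against the IMP only, so nothing records that the challenge was the likely cause of a reportable event.
- The exemption names the 150% challenge. Section 11.3.1 defines a different challenge for patients on intestinal infusion, so its reach for them is unclear.

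**Step 4: count.** The inputs are 24 randomized patients (Section 9.3) and 3 challenges each (Section 11.3.1), with no drop-out or replacement.
- All challenges: 24 × 3 = 72.
- Visit 2: 24 × 1 = 24, and 24/72 = 33%. Any harm starting before the first tablet falls outside AE and SAE collection.
- Visits 6 and 7: 24 × 2 = 48, and 48/72 = 67%. Only challenge dyskinesia is exempt.

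**Step 5: what the SAP would do with a Visit 2 event once it counts as an AE.**
- Tables AE 1 to AE 4 (SAP 10.2.2.1) have no treatment-emergent filter, and AE 3 and AE 4 define up-titration as everything up to Visit 6. A pre-IMP event would be counted in a treatment column.
- SAP Section 5.9 imputes a missing AE start time to just after first IMP intake. An untimed Visit 2 challenge event would be moved onto study drug.
- The FAS requires dosing (SAP Table 1). A patient harmed by the challenge and never dosed would be outside every FAS table and listing, including medical history.

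**The case against.** A reader might infer that harm from the challenge is kept out of AE and SAE reporting at all three visits. The documents do not support that. At Visits 6 and 7 the exemption covers dyskinesia worsening alone, and a fall, fracture, syncope or hallucination after those challenges remains reportable.

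A reader might also infer a rule that challenge dyskinesia is exempt even if serious. No such rule is written. The carve-out has a plain purpose: the challenge is given to provoke dyskinesia for rating. Section 11.2.1.2 also asks for caution when seriousness is in doubt. That instruction concerns whether an AE is serious, however, so it does not clearly reach an event that has been excluded from being an AE.

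Four further points stand in part:
- Challenge dyskinesia is not lost. It is rated at about 30, 60 and 90 minutes, videotaped, entered in the eCRF and analysed as efficacy data. Those ratings carry no seriousness field and trigger no alert.
- Visit 2 events are recorded and, for dosed patients, tabulated as medical history. What they lack is grading, causality and expedited reporting. The interval is short, and events starting after the first tablet on Day 1 are AEs.
- Section 11.1.10 equates its interval with the screening period, while Table 8.1-1 gives screening as Day -28 to Day -5 and labels Day 1 as baseline. The clause may not have been written with the Visit 2 challenge in mind. That makes the conflict with the synopsis more important to settle.
- It would be wrong to say that every patient receives more L-DOPA than usual. The 250 mg cap can remove the increase, Section 11.3.1 notes that the morning dose is generally also around 150%, and Section 8.3 describes such challenges as routine practice.

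**Conclusion.** The point holds in a limited form. The synopsis and the body text disagree on when AE collection opens. Under the body text, harm starting between the Visit 2 challenge and the first tablet is neither an AE nor an SAE, however serious. This affects 24 of 72 planned challenges, assuming 24 completers, no replacements and the inferred order of challenge before IMP. At the other 48 the gap is confined to challenge dyskinesia that meets a seriousness criterion, and it arises from missing wording, not from a stated exclusion.

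The documents give no rate of harm from the challenge, so no expected number of unreported events can be stated. Events before the first IMP dose cannot be caused by the IMP, so the Visit 2 gap concerns safety oversight and not the comparison of NLX-112 with placebo. The Visits 6 and 7 gap does touch that comparison, because a serious event on treatment could be absent from a primary endpoint. The change should be made. The point does not call the design into question.

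**What to change.** **Protocol**
- Reconcile the synopsis with Sections 11.1.10 and 11.2.1.6 and footnote 13 of Table 8.1-1, so that AE and SAE collection opens at the start of the Visit 2 challenge. Flag events with onset before the first tablet as pre-IMP, and record the times of the challenge, the first tablet and event onset.
- In Section 11.2.1.1, state that the dyskinesia exemption does not apply to an event that meets an SAE criterion, and whether it covers the challenge used for infusion patients. Expected, non-serious challenge dyskinesia stays exempt, so Visit 2 would not fill the AE log.
- In Section 11.2.1.8, record causality to the challenge beside causality to the IMP.

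**SAP**
- List pre-IMP events separately, for all challenged patients and not only the FAS.
- Restrict Tables AE 1 to AE 4 to events starting at or after first IMP intake.
- Exclude events flagged pre-IMP from the start-time imputation in Section 5.9.

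**Cost.** One or two eCRF fields, one extra listing, protocol wording and minor SAP edits. The SAP edits are needed: without them, pre-IMP events would enter the treatment columns. No dose, visit or assessment changes.

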### **11.2 Assessments related to primary endpoints**

#### **11.2.1 *Adverse events***

The Principal Investigator is responsible for ensuring that all medical staff involved in the study is familiar with the content of this section and the content of the standard operating procedures (SOPs) of each site regarding emergencies.

##### **11.2.1.1 *Definition of adverse event***

An AE is defined as any untoward medical occurrence in a patient administered a medicinal product and which does not necessarily have a causal relationship with this treatment. An AE can therefore be any unfavorable and unintended sign (including an abnormal laboratory finding), symptom, or disease temporally associated with the use of a medicinal product, whether or not considered related to the medicinal product.

Worsening of dyskinesias (except those associated with the 150% L-DOPA challenge) or PD symptoms compared to baseline will be reported as AEs.

#### *11.2.1.2 Definition of serious adverse event*

An SAE is any AE which:

- results in death,
- is life-threatening (this refers to a reaction in which the patient was at risk of death at the time of the reaction; it does not refer to a reaction that hypothetically might have led to death if the reaction was more severe),
- requires in-patient hospitalization or prolongation of existing hospitalization,
- results in persistent or significant disability/incapacity,
- is a congenital anomaly/birth defect,
- is an important medical event (IME) (this refers to a reaction that may not be immediately life-threatening or result in death or hospitalization, but may jeopardize the patient or may require intervention to prevent any of the other outcomes defined above).

Examples of IMEs are intensive treatment in an emergency room for allergic bronchospasm or blood dyscrasias, convulsions that do not result in hospitalization, development of drug dependency, and drug abuse.

Planned hospitalizations or surgical interventions for a condition that existed before the patient signed the ICF and that did not change in intensity are not SAEs.

If there is any doubt as to whether an AE meets the definition of an SAE, a conservative viewpoint must be taken, and the AE must be reported as an SAE.

